4.4.4. Regulatory Authority Approval

The Sponsor will obtain approval to conduct the trial from the appropriate regulatory agency in accordance with any applicable country specific regulatory requirements before any site may initiate the trial in that country.

5. OBJECTIVES AND ENDPOINTS

The primary, secondary, and exploratory objectives and endpoints are provided in [Table 2](#).

Table 2: Objectives and Endpoints

Primary Objective	Primary Endpoint

 To evaluate the efficacy of rademikibart compared to placebo as an adjunct to standard therapy on the treatment failure rate within 28 days after randomization in participants with COPD and an eosinophilic phenotype experiencing an acute COPD exacerbation. 	
 Treatment failure rate within 28 days after randomization.
Secondary Objectives	Secondary Endpoints

 To evaluate the efficacy of rademikibart compared to placebo as an adjunct to standard therapy on subsequent COPD exacerbations in participants with COPD and an eosinophilic phenotype experiencing an acute COPD exacerbation. 	
 Rate of new moderate and severe COPD exacerbations over the 28 days after randomization. Time to the first new moderate or severe COPD exacerbation in the 28 days after randomization. Mean CFB in clinical respiratory symptoms of COPD using the E-RS: COPD comprised in the EXACT-PRO through Week 1, Week 2, and Week 4. Absolute CFB in post-BD FEV₁ at Day 3, Week 1, and Week 4.

 To evaluate the safety of rademikibart compared to placebo when administered as an adjunct to standard therapy in participants with COPD and an eosinophilic phenotype experiencing an acute COPD exacerbation. 	
 Incidence of AEs, including SAEs, AESIs, and DILI reported. Incidence of UADEs. Incidence of injection site reactions. Changes in safety laboratory parameters. Changes in vital signs, physical examinations, and ECG parameters.
Exploratory Objectives	Exploratory Endpoints

 To further evaluate the efficacy of rademikibart compared to placebo as an adjunct to standard therapy on subsequent COPD exacerbations in participants with COPD and an eosinophilic phenotype 	
 Proportion of participants with at least 1 moderate or severe acute COPD exacerbation (subsequent to the index acute COPD exacerbation) through Week 4 and Week 8.


experiencing an acute COPD exacerbation.
	
 • Rate of moderate and severe COPD exacerbations (subsequent to the index exacerbation) over the 8-week period compared to placebo. • Acute exacerbation rate (all subsequent COPD exacerbations) over the 8-week period compared to placebo.

 • To evaluate the incidence of immunogenicity (anti-rademikibart antibodies: ADAs and nAbs) in participants with COPD and an eosinophilic phenotype experiencing an acute COPD exacerbation. 	
 • Incidence and duration of treatment-emergent ADAs and nAbs.

 • To evaluate the PK of rademikibart in participants with COPD and an eosinophilic phenotype experiencing an acute COPD exacerbation. 	
 • PK concentrations and, if calculable, PK parameters of rademikibart.

 • To evaluate the pharmacodynamics of rademikibart in participants with COPD and an eosinophilic phenotype experiencing an acute COPD exacerbation. 	
 • CFB in FeNO. • CFB in biomarkers in the blood (including but not limited to peripheral blood eosinophil count, eotaxin-3, CRP, total immunoglobulin E, TARC, and PARC).

 • To evaluate the effect of rademikibart compared with placebo as an adjunct to standard therapy on lung function in participants with COPD and an eosinophilic phenotype experiencing an acute COPD exacerbation. 	
 • Change from the earliest available measurements in pre-BD FEV₁ (absolute and percent changes, percentage predicted) at Week 1, Week 4, and Week 8. • CFB in post-BD FEV₁ at Day 1 and Day 2, and during the Follow-up Period at Week 8. • CFB or the earliest available measurements in other lung function measurements: pre-BD and post-BD FVC and FEV₁/FVC at scheduled timepoints.

 • To evaluate the effect of rademikibart compared with placebo as an adjunct to standard therapy on healthcare resource 	
 • Length of stay in an urgent healthcare facility, ED, or hospital (hours).


utilization in participants with COPD and an eosinophilic phenotype experiencing an acute COPD exacerbation.
	
• Time to ready-for-discharge in hospitalized participants based on clinical assessment.• Time to ready-for-discharge in hospitalized participants based on VBG results• Total number of COPD-related hospital-stay hours during the first 28 days after discharge from the index acute COPD exacerbation (may include more than 1 COPD-related admission to the hospital).• Total number of COPD-related hospital-stay hours during the 8-week trial period (may include more than 1 COPD-related admission to the hospital).• For hospitalized participants: Hospital readmission rate during the first 28 days after discharge from the index acute COPD exacerbation and during the 8-week trial period.• Total number of all-cause hospital-stay hours during the first 28 days after discharge from the index acute COPD exacerbation (may include more than 1 admission to the hospital).• Total number of all-cause hospital-stay hours during the 8-week trial period (may include more than 1 admission to the hospital).• Incidence and rate of unscheduled visits for urgent care primarily related to COPD symptoms.• Incidence and rate of unscheduled calls for urgent care primarily related to COPD symptoms.• ICU admission rate during the first 4-week trial period.• Invasive ventilation rate during the first 4-week trial period.
---	---

 To explore the effect of rademikibart compared with placebo as an adjunct to standard therapy on improvement in symptoms, usage of rescue medications, and health-related quality of life/PROs in participants with COPD and an eosinophilic phenotype experiencing an acute COPD exacerbation. 	
 CFB in Dyspnea NRS at scheduled timepoints. Total dose/use of systemic corticosteroids. Use of daily puffs of rescue medication. CFB in SGRQ total score compared to placebo at Weeks 4 and 8. Proportion of participants with SGRQ improvement ≥ 4 points at Week 4 and Week 8. CFB in CAT total score compared to placebo at Week 1, Week 4, and Week 8. Proportion of participants with a decrease from Baseline in CAT total score ≥ 2 at Week 1, Week 4, and Week 8. CFB in clinical respiratory symptoms of COPD using the Evaluating Respiratory Symptoms in COPD (E-RS: COPD) comprised in the EXACT-PRO tool during the Follow-up Period at Week 8.
---	---

ADA = anti-drug antibody; AE = adverse event; AESI = adverse event of special interest; BD = bronchodilator; CAT = COPD Assessment Test; CFB = change-from-baseline; COPD = chronic obstructive pulmonary disease; CRP = C-reactive protein; DILI = drug-induced liver injury; ECG = electrocardiogram; ED = emergency department; E-RS: COPD = Evaluating Respiratory Symptoms in COPD; EXACT-PRO = Exacerbations of Chronic Obstructive Pulmonary Disease Tool- PRO; FeNO = fractional exhaled nitric oxide; FEV₁ = forced expiratory volume in 1 second; FVC = forced vital capacity; ICU = intensive care unit; IgE = immunoglobulin E; nAb = neutralizing antibody; NRS = numerical rating scale; PARC = pulmonary and activation-regulated chemokine; PK = pharmacokinetic(s); PRO = patient-reported outcome; SAE = serious adverse event; SC = subcutaneous; SGRQ = St. George's Respiratory Questionnaire; TARC = thymus and activation-regulated chemokine; UADE = unanticipated adverse device effect; VBG = venous blood gas

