Based on the available evidence in COPD patients with an eosinophilic phenotype, it is anticipated that a fully human monoclonal antibody that blocks the shared receptor component for IL-4 and IL-13, key and central drivers of type 2 inflammation, could acutely treat eosinophilic exacerbations of COPD. However, this approach has not yet been tested. Given the recent promising findings in patients with eosinophilic exacerbations from the ABRA trial (Ramakrishnan, Russell, et al. 2024), the rapid improvements in lung function with rademikibart (Kerwin et al. 2024), as well as the significant unmet medical needs in treating a COPD exacerbation, it is worth investigating whether eosinophilic exacerbations of COPD could be treated acutely with rademikibart.

Rademikibart has demonstrated efficacy and safety across various diseases associated with type 2 inflammation including asthma. In the Phase 2 trial in patients with persistent asthma, participants treated with rademikibart demonstrated significant improvements in lung function by Week 1 and was sustained through Week 24, as measured by in-clinic spirometry. A subgroup analysis of “COPD-like” patients (eg, patients with age of onset asthma > 40 years and post-BD FEV₁/FVC 0.7) showed similar treatment effects compared to the overall population.

In an exploratory post-hoc analysis of this trial, the absolute change from baseline (CFB) in pre-BD FEV₁, derived from self-administered at-home spirometry on Days 1 through 7, was analyzed in participants with baseline eosinophil counts ≥ 300 cells/ μ L. In this subpopulation, 77% of the Week 1 improvement in pre-BD FEV₁ was achieved within 24 hours post-dose (FEV₁ CFB: 93 mL improvement vs -101 mL for placebo), with 84% of the total improvement realized by Day 2. This post hoc analysis demonstrates that rademikibart delivers rapid and significant

lung function improvement, with notable gains within 24 hours of a single 600 mg loading dose. These findings highlight rademikibart's potential as a fast-acting, effective therapy for type 2 inflammation-driven airway disease and suggest its possible utility in early treatment following acute exacerbations of asthma or COPD.

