6.3. Treatment Assignment

Participants will be randomized in a 1:1 ratio to 1 of the following double-blinded treatment groups, stratified by severity of the acute COPD exacerbation (requiring hospitalization or not [yes/no]) at baseline, and baseline smoking status [current or former]:

- **Rademikibart** 600 mg dose administered as 4 SC injections of 1 mL (150 mg) each.
- **Matching Placebo** administered as 4 SC injections of 1 mL each.

IP (rademikibart 600 mg SC or placebo SC) will be administered on Day 0 as per the SoA (Table 5).

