10.3. Spirometry

Spirometry will be performed according to American Thoracic Society (ATS)/European Respiratory Society (ERS) guidelines (Miller et al. 2005; Graham et al. 2019) at the timepoints specified in the SoA (Table 5). Spirometry assessments, including FEV₁, and FVC (both the absolute measurement and the percentage of predicted normal value will be recorded), should be made as close to the scheduled timepoints as possible. In addition, protocol-specified clinic spirometry must be completed in accordance with the lifestyle restrictions as defined in Section 7.3.

Spirometry will be performed preferably in the morning; afternoon is allowable in the exceptional circumstance when morning spirometry cannot be performed. Current smokers need to be reminded not to smoke for at least 1 hour before spirometry. For each participant, the same spirometer and standard spirometric techniques, including calibration, will be used to perform spirometry at all visits and, whenever possible, the same person should perform the measurements.

Baseline FEV₁ is defined as the post-BD FEV₁ performed at Visit 2 before IP administration. If Visit 1b and Day 0 (Visit 2) are the same day, then post-BD spirometry does not need to be repeated.

At the timepoints SoA (Table 5), if the participant's condition allows, post-BD FEV₁ will be conducted approximately 15 to 30 minutes after the participant-administers 4 inhalations of albuterol (salbutamol) via MDI (ie, total of 400 mcg) using a spacer device.

It is anticipated that participants who are randomized into the trial will receive albuterol (salbutamol) as part of the routine treatment of the acute COPD exacerbation during Visit 2. In this case, spirometry should be scheduled to coincide with this treatment to allow post-BD recordings to be measured.

For hospitalized participants, post-BD spirometry should also be performed at the timepoints specified in the SoA (Table 5), including V3 and V4, provided the participant's condition allows.

Hospitalized participants discharged from the hospital prior to Visit 3 and Visit 4, or participants that were not hospitalized for the index COPD exacerbation, should return to the trial site or have a home health care visit for spirometry assessments at Visit 3 and Visit 4 when feasible.

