If the participant can tolerate BD washout, at Visit 6, Visit 8, Visit 9, and on the day of discharge (only for hospitalized participants), spirometry will be performed prior to administering maintenance COPD medication(s) (pre-BD) and post-BD (as defined above). Participants should withhold their usual maintenance therapies on the day(s) when pre-BD spirometry is being performed as below:

- Withholding the last dose of salbutamol/albuterol or levosalbutamol/levalbuterol for at least 6 hours,
- Withholding the last dose of LABA for at least 12 hours [ultra-long-acting LABA like vilanterol should be withheld for at least 24 hours]
- Withholding the last dose of ipratropium bromide for at least 8 hours
- Withholding the last dose of LAMA for at least 24 hours

This washout period will be verified before performing the measurements. After completing the pre-BD spirometry, the post-BD spirometry should follow the steps as that at Visit 2 before IP administration.

Where multiple assessments are scheduled at the same time point, the sequence of assessments should ideally be as shown below. However, during the Screening Visit (Visit 1b) and/or the Randomization Visit (Visit 2), this order may be modified as needed, including instances where some or all of these procedures are performed as part of routine/urgent/ inpatient hospitalized care.

- PROs and other questionnaires.
- Vital signs.
- 12-lead ECG.
- FeNO.
- Spirometry assessment (pre-bronchodilator).
- Post-bronchodilator spirometry.
- e-diary download.
- Blood sampling and laboratory assessments.
- IP administration (only applicable to Visit 2).

Further details on spirometry will be available in a separate operational manual provided to the sites.

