- n* Screening Visit 1b: Due to the short screening window, local laboratory results will be used for the purpose of determining the participant's eligibility for randomization. Local laboratory samples should be taken at Screening Visit 1b and the results should be received and reviewed prior to randomization to allow review of the applicable eligibility criteria. If local laboratory results from the assessment of the current COPD exacerbation are already available within 72 hours prior to Screening Visit 1b, these results can be used for determination of participant's eligibility. For all randomized participants, a sample for central laboratory analysis should be obtained before IP administration on Day 0 as baseline.
- o* For women of childbearing potential, must be negative prior to IP administration. Analyzed at a local laboratory.
- p* For women of childbearing potential, analyzed at a local laboratory. Visit 2 collection is only required if Screening and the Baseline Visit (Day 0) are not on the same day.
- q* On Day 0, PK and ADA/nAb samples will be collected prior to administration of IP. On days when PK and ADA/nAb sample collection are coinciding, the samples can be taken at the same time.
- r* Venous blood gas will only be assessed in hospitalized participants.
- s* Spirometry assessments include FEV₁, and FVC (both the absolute measurement, and the percentage of predicted normal value will be recorded. Spirometry will be performed preferably in the morning; afternoon is allowable in the exceptional circumstance when morning spirometry cannot be performed. If the participant can tolerate BD washout, at Visit 6, Visit 8, Visit 9, and on the day of discharge (only for hospitalized participants), pre-BD spirometry will be performed prior to administering maintenance COPD medication(s). Participants should withhold their usual maintenance therapies on the day(s) when pre-BD spirometry is being performed as below: Withholding the last dose of salbutamol/albuterol or levosalbutamol/levalbuterol for at least 6 hours; withholding the last dose of LABA for at least 12 hours (ultra-long

- acting LABA like vilanterol should be withheld for at least 24 hours); withholding the last dose of ipratropium bromide for at least 8 hours; withholding the last dose of LAMA for at least 24 hours. This washout period will be verified before performing the measurements.

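### The exploratory pre-bronchodilator lung-function endpoints use the earliest available value as reference, and as scheduled that value is post-dose

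*Protocol*

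**What the plan says.** Section 5, Table 2 lists, among the exploratory lung-function endpoints, "Change from the earliest available measurements in pre-BD" FEV1, expressed as absolute change, percent change and percent predicted, at Weeks 1, 4 and 8. The next lung-function bullet but one covers pre-BD and post-BD FVC and FEV1/FVC and reads "CFB or the earliest available measurements in other lung function measurements".

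Section 10.3 gives the pre-BD timepoints, conditional on the participant tolerating washout: "at Visit 6, Visit 8, Visit 9, and on the day of discharge (only for hospitalized participants), spirometry will be performed" before maintenance medication and again after bronchodilator. Footnote s of the Schedule of Assessments (Appendix A) repeats the list: "Visit 9, and on the day of discharge (only for hospitalized participants), pre-BD spirometry will be performed". Section 6.1 also asks for pre-BD and post-BD measurements on the morning of discharge.

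Section 6.3 fixes dosing: the single dose "will be administered on Day 0 as per the SoA".

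The only FEV1 baseline that the protocol defines is the post-BD value "performed at Visit 2 before IP administration" (Section 10.3). Sections 8.2.2.3 and 10.3 expect albuterol to be part of routine care around randomisation, and time the spirometry to it so that post-BD values are captured.

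**The concern.** A change-from-reference endpoint measures a treatment effect only if the reference precedes treatment. Here the schedule provides no pre-BD measurement before the dose, so the earliest available pre-BD value is, for anyone tested as scheduled, already a post-dose value. Whatever the drug has achieved by then is in the reference and is subtracted.

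Two consequences follow. In the non-hospitalised stratum the reference and the Week 1 result are the same measurement. In the hospitalised stratum the reference day is the discharge day, a post-randomisation event that treatment may influence; Table 2 itself lists time to ready-for-discharge as an outcome. The arms then need not share a comparable reference.

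At stake is the reading of pre-BD FEV1, the measure on which Section 4.3.2 rests its rapid-onset rationale. A near-zero between-arm difference on this endpoint could be taken as absence of effect when it comes from the definition.

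**Working it through.** The protocol states no sample size or power for these endpoints, so there is no planned figure to reproduce. The check sets the schedule against the definition.

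**Timing of every scheduled pre-BD test (Section 10.3; footnote s)**
- Dose: Visit 2, Day 0.
- Visit 6: Day 7 (Week 1). Visit 8: Day 28 (Week 4). Visit 9: Day 56 (Week 8).
- Discharge day: hospitalised participants only, after Day 0 dosing.

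No listed pre-BD test precedes the dose. Both Section 10.3 and footnote c say that, when Visits 1b and 2 fall on the same day, post-BD spirometry need not be repeated; neither mentions a pre-BD test there.

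**What the endpoint then measures**
Let Y(t) be the pre-BD value at time t and r the time of the earliest available value. The endpoint is Y(t) − Y(r). If τ(t) is the between-arm difference at time t and all participants share the same r, the expected between-arm difference in change is τ(t) − τ(r).

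- Non-hospitalised, first pre-BD value at Visit 6: Week 1 change = Y(W1) − Y(W1) = 0 mL in both arms. Week 4 estimates τ(W4) − τ(W1) and Week 8 estimates τ(W8) − τ(W1). An effect complete by Week 1 and then maintained gives a difference of 0 at every visit.
- Non-hospitalised, washout not tolerated at Visit 6: Week 1 is missing and the Week 4 change is 0 by the same identity.
- Hospitalised, discharged on day d before Visit 6: Week 1 estimates τ(W1) − τ(d), with d varying by participant and possibly by arm.
- Hospitalised, discharged on or after the Visit 6 test: the Week 1 change is again 0.

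**Illustration of size (Section 4.3.2)**
The post hoc asthma analysis gives a 24-hour change of +93 mL on active and −101 mL on placebo, described as 77% of the Week 1 improvement, "with 84% of the total improvement realized by Day 2".

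- Difference at 24 hours: 93 − (−101) = 194 mL.
- Implied Week 1 effect: 93/0.77 ≈ 121 mL if the 77% refers to the active-arm change; 194/0.77 ≈ 252 mL if it refers to the difference from placebo. The text does not say which.
- Left with a Day 1 discharge reference: 1 − 0.77 = 23%, about 28 to 58 mL.
- Left with a Day 2 discharge reference: 1 − 0.84 = 16%, about 19 to 40 mL.
- Left at Week 1 with a Visit 6 reference: 0 mL.

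The last line does not depend on the asthma figures; the others do.

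**The case against.** **A pre-dose pre-BD value may exist.** The spirometry rows of the Schedule of Assessments are not visible in the text reviewed, so a pre-BD entry at Visit 1a, 1b or 2 cannot be excluded. Footnote b lets spirometry done in the care of the exacerbation serve for Screening, and the order-of-assessments list in Section 10.3, which may be altered at Visits 1b and 2, includes a pre-BD step. This stands as a limit: it is not established that every non-hospitalised participant has a zero Week 1 change. But Section 10.3 and footnote s agree on a post-dose-only list, the order-of-assessments list schedules nothing, and the spirometry in inclusion criterion 6 is post-BD. Occasional pre-dose values would leave the endpoint mixing pre-dose and post-dose references.

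**The asthma figures do not transfer.** A reader might infer that 194 mL would be lost in this trial. The documents do not support that: the figures come from a post hoc analysis of home spirometry in persistent asthma with eosinophils of at least 300 cells/µL, not from COPD exacerbations treated with systemic corticosteroids.

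**Early benefit is measured elsewhere.** A reader might also infer that the trial cannot show a rapid lung-function effect. That is not so. Post-BD FEV1 is compared with a pre-dose Visit 2 baseline at Day 3, Week 1 and Week 4 as a secondary endpoint, and at Days 1 and 2 and Week 8 as an exploratory one.

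**The SAP could settle it.** The SAP can set data conventions, but it cannot create a pre-dose measurement. Following Table 2 as written reproduces the problem. The FVC and FEV1/FVC bullet does offer change from baseline as an alternative, but the schedule shows no pre-dose pre-BD baseline for it to use.

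**Conclusion.** The definition is wrong as written for the pre-BD measures. For participants tested as Section 10.3 schedules, the reference is a post-treatment value. In the non-hospitalised stratum the Week 1 change is zero by construction, and Weeks 4 and 8 show only change after Week 1. In the hospitalised stratum the reference day follows discharge timing, and the direction of any resulting bias cannot be stated in advance.

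This rests on one assumption: that no pre-dose pre-BD value exists, either from routine care or in the schedule rows not visible. Where one exists for a participant, the zero does not apply to that participant. The protocol neither requires nor defines such a value.

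The reach is limited to exploratory endpoints: pre-BD FEV1, and pre-BD FVC and FEV1/FVC where the same reference is used. The primary endpoint, the sample size and the post-BD FEV1 endpoints are untouched. The point should be corrected, but it does not threaten the trial's main conclusions.

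**What to change.** In Table 2, replace change from the earliest available measurement, for pre-BD FEV1, FVC and FEV1/FVC, with the observed pre-BD value at Weeks 1, 4 and 8. Compare arms with the mixed model or analysis of covariance that Section 13.4.7 already plans for continuous exploratory endpoints, adjusted for the corresponding pre-dose Visit 2 post-BD value, the two stratification factors and visit. State that no post-dose value may serve as the reference, whether subtracted or entered as a covariate. FEV1 can still be reported in absolute units and as percent predicted; percent change has no systematic pre-dose pre-BD denominator and should go. Any pre-dose pre-BD values from routine care can be listed.

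Post-BD FVC and FEV1/FVC keep their change from the Visit 2 baseline.

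The cost is a wording change in Table 2 and a matching entry in the SAP, made before unblinding. It needs no new measurement and changes no clinical procedure.

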10.1. Treatment Failure

Treatment failure is defined as death due to any cause, (re)admission to a hospital for COPD, ED (re)visit or unscheduled medical visit for worsening of COPD symptoms, or the necessity to intensify pharmacologic treatment (including second course of systemic steroids for COPD exacerbation) within 28 days after randomization.

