13.4. Statistical Analyses

13.4.1. General Considerations

Unless otherwise stated, all significance tests will be 2-sided using the 5% significance level. In addition, 95% confidence intervals will be provided where appropriate.

An observed-cases approach will be used for tabulations of data by visit (ie, involving only those participants who attended each specific visit).

Categorical data will be summarized using the number and percentage of participants in each category and treatment group. Continuous data will be summarized using descriptive statistics including the number of non-missing observations (n), mean, standard deviation, minimum, 25th percentile, median (50th percentile), 75th percentile, and maximum values.

All the analyses specified in the protocol will be reviewed in relation to the blinded data obtained and the SAP will be finalized before breaking the randomization code for primary analysis. Any changes from the statistical analysis planned in this clinical trial protocol will be described and justified in a protocol amendment, the SAP, and/or in the CSR.

Objectives and endpoints are provided in Section 5.

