13.4.7. Exploratory Efficacy Endpoints

The exploratory efficacy endpoints are provided in Section 5.

Exploratory efficacy endpoints will be summarized by treatment group and visit using descriptive statistics. Cochran-Mantel-Haenszel chi-square tests will be used to compare treatment groups with respect to the proportion-based binary efficacy endpoints and a mixed model repeated measures or analysis of covariance will be used to compare treatment groups with respect to continuous efficacy endpoints. Negative binomial models will be used for any exploratory analyses of exacerbation rates, and stratified log-rank test will be used for any time-to-event driven exploratory analyses. Analyses will be conducted based on observed data using the FAS.

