13.6. Handling of Missing Data

Missing data handling is described in the Sensitivity Analyses for primary endpoint in Section [13.4.5.1](#).

Additional details will be provided in the SAP.

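### The exploratory SGRQ and CAT responder proportions use observed data, so participants who die before the visit leave the denominator although their non-response is known

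*Protocol*

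**What the plan says.** Table 2 (protocol Section 5) includes two responder endpoints among the exploratory endpoints:

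- SGRQ: "Proportion of participants with SGRQ improvement ≥ 4 points at Week 4 and Week 8".
- CAT: "Proportion of participants with a decrease from Baseline in CAT total score" of at least 2 points, at Weeks 1, 4 and 8.

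Section 13.4.7 sets the test and the data basis. "Cochran-Mantel-Haenszel chi-square tests will be used to compare treatment groups with respect to the proportion-based binary efficacy endpoints", and "Analyses will be conducted based on observed data using the FAS".

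Section 13.4.1 shows what observed cases means for data presented by visit: "An observed-cases approach will be used for tabulations of data by visit (ie, involving only those participants who attended each specific visit").

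On missing data, Section 13.6 says "Missing data handling is described in the Sensitivity Analyses for primary endpoint in Section" 13.4.5.1, and then "Additional details will be provided in the SAP". The rules in Section 13.4.5.1 concern the primary endpoint only.

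Death enters an efficacy outcome explicitly in Section 10.1: "Treatment failure is defined as death due to any cause", among other components, within 28 days after randomization. No section gives a similar rule for the SGRQ or CAT responder endpoints.

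**The concern.** A responder proportion asks how many of the participants in an arm improved by a set amount. For a participant who died before the visit the answer is known: no improvement occurred. Treating that participant as missing turns the endpoint into a proportion among survivors with a score. Survival is determined after randomization, so the two denominators need no longer be comparable. For a given response rate among survivors, the arm with more deaths gets a higher percentage than it would if deaths counted as non-response.

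The primary endpoint covers this only in part. It counts deaths up to Day 28, whereas both responder endpoints run to Week 8. A death between Day 29 and Day 56 is not a primary failure, and under the stated rule it also leaves the Week 8 responder proportions.

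What is at stake is the reading of two supportive patient-reported endpoints, not the trial's main conclusion.

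**Working it through.** **The text.** Section 13.4.7 puts the responder comparison on observed data. Section 13.4.1 limits by-visit tabulations to attendees. Section 13.6 points to missing-data rules for the primary endpoint only. Together they leave a participant who died before Week 1, 4 or 8 out of that visit's proportion.

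**The plan's own figures.** The protocol states no responder rate, death rate or power for these endpoints, so there is no figure to reproduce. The only document input is 160 randomized 1:1 (Sections 6.2 and 6.3), or 80 per arm. Everything else below is an assumption.

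**Formulas.** Let r1 and r0 be the response rates among survivors on rademikibart and placebo, and d1 and d0 the proportions who die before the visit. Assume no other missing scores.

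- Observed-data difference: r1 − r0.
- Difference with death as non-response: r1(1 − d1) − r0(1 − d0).
- With r1 = r0 = r, the first is 0 and the second is r(d0 − d1).

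**Death rates between 2% and 10%, r = 0.60**

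| Deaths, placebo | Deaths, rademikibart | Observed data | Death as non-response |
|---|---|---|---|
| 5% | 2% | 0 | 0.588 − 0.570 = +1.8 points |
| 10% | 5% | 0 | 0.570 − 0.540 = +3.0 points |
| 2% | 5% | 0 | 0.570 − 0.588 = −1.8 points |

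**Death counts per arm of 80, r from 0.40 to 0.60** (shift = r × difference in deaths / 80)

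| Deaths, rademikibart vs placebo | Shift in the difference |
|---|---|
| 0 vs 2 | +1.0 to +1.5 points |
| 1 vs 4 | +1.5 to +2.2 points |
| 0 vs 4 | +2.0 to +3.0 points |
| 0 vs 8 | +4.0 to +6.0 points |
| 4 vs 4 | 0, but each arm's rate falls by 2 to 3 points |

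The sign reverses if the extra deaths fall on rademikibart. The 0 vs 8 row is an extreme: 10% mortality in one arm and none in the other.

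**Against sampling error.** At r = 0.60 and 80 per arm, the standard error of the difference is √(2 × 0.6 × 0.4 / 80) = √0.006 = 0.0775, or about 7.7 points. Shifts of 1.8 and 3.0 points are 1.8 / 7.7 = 0.23 and 3.0 / 7.7 = 0.39 standard errors.

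**The case against.** **The protocol never says that deaths are excluded, and the primary analysis in Section 13.4.5 is also based on observed data although death counts there.** The parallel fails. Death is a component of the primary endpoint, so a death is itself an observed outcome. The SGRQ and CAT responder definitions rest on a score alone, and a participant who has died has none.

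**This is detail for the SAP.** Section 13 calls itself a summary, and Section 13.6 defers further missing-data detail. Silence in the protocol would indeed be no finding. But Section 13.4.7 is not silent: it chooses observed data. A later rule counting deaths as non-response would depart from that choice. Section 13.4.1 allows such a change if it is described and justified, so the remedy is easy, but the stated rule is still the one to correct.

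**The weight is low.** This stands. The endpoints are exploratory and have no multiplicity adjustment (Section 13.4.2).

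Three stronger readings are tempting but not supported:

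- *The responder results could overturn or seriously contradict the primary result.* They play no part in it, and the shifts above are a fraction of a standard error.
- *A mortality imbalance would be hidden.* Deaths to Day 28 are primary failures (Section 10.1), and deaths are summarized by treatment group (Section 13.4.8.1).
- *High mortality is to be expected here.* The 10% inpatient mortality in Section 4.3.2 is cited background, not an estimate for this sample. Exclusion 19 in Section 7.2 removes participants with, for example, respiratory failure needing ventilation or impending intensive care admission, where the investigator judges that it would interfere with evaluation.

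Finally, a rule for deaths does not restore the full randomized comparison. Participants who withdraw or are too ill to attend also lack scores. That limit is real, and is why the fix includes a sensitivity analysis.

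**Conclusion.** The point holds as a minor one. As written, Sections 13.4.7 and 13.4.1 drop participants who die before the visit from the SGRQ and CAT responder proportions, although their non-response is known.

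The likely effect on the arm difference is about 2 to 3 points. This rests on assumed death rates of 2% to 10%, a 60% response among survivors in both arms, and no other missing scores. None of these values comes from the protocol. Equal deaths leave a zero difference at zero. The direction cannot be known in advance, so this is not a bias in favour of rademikibart. The primary analysis and the sample size are untouched.

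The correction is still worth making, because it costs almost nothing and brings deaths between Day 29 and Day 56 into the Week 8 responder comparison.

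**What to change.** Add to Section 13.4.7: for the SGRQ and CAT responder endpoints, a participant who died from any cause before the visit is a non-responder at that visit and remains in the FAS denominator. Other missing scores stay on the observed-data basis in the main analysis. A sensitivity analysis counts all other missing scores as non-response too.

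The change should be made before unblinding, so that it cannot appear data-driven. It needs one or two sentences and a few lines of programming, with no new data, visits or participants. The downside is that reported responder percentages will be slightly lower.
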